3.5. DETERMINATION OF SAMPLE SIZE

The sample size for this study is not based on statistical justification. Recruitment of mtDNA-PMM subjects will be limited to those subjects who participated in REN001-201 or REN001-101, and reside in countries where this long-term safety study is approved. It is estimated that approximately 150 mtDNA-PMM subjects will be enrolled.

It is anticipated that up to 50 nDNA-PMM subjects may also be enrolled.

3.6. TREATMENT ASSIGNMENT AND BLINDING

REN001-202 is an open label study with all subjects receiving mavodelpar 100 mg once daily. Prior treatment allocation in REN001-201 will remain blinded until database lock of REN001-201.

Subjects enrolling from REN001-201 will be assigned the same subject ID they were allocated in REN001-201. Subjects enrolling from study REN001-101 and nDNA-PMM subjects will be assigned a new unique 6-digit subject ID.

A subject, enrolling under pathway options 3 or 4 ([Section 3.3](#)), may be rescreened once with prior Sponsor approval and will be given a new subject ID (their original subject ID will be recorded).

3.7. ADMINISTRATION OF STUDY MEDICATION

Subjects will receive 100 mg mavodelpar orally once daily. Study drug should be taken with food at a convenient time to the subject (ideally in the morning). The exceptions to this are:

- at the Baseline visit for subjects enrolled under pathway options 2-4 ([Section 3.3](#)) the first dose will be taken with food at the site under the supervision of site staff. Subjects enrolled under pathway option 1 are expected to have taken their last dose of REN001-201 study medication that morning prior to their REN001-201 Week 24 (REN001-202 Baseline) visit, in which case their first dose of mavodelpar in REN001-202 should be taken the following day.
- at the Month 3 visit, where the subject should take the study drug at the study centre with food, when instructed to do so by the site staff.

3.8. APPROACH TO COMBINING REN001-201 DATA

For mtDNA-PMM subjects, the data from REN001-202 will be combined with data from its feeder study, REN001-201. The combined data will be presented from the start of REN001-201 and from the start of REN001 treatment. Presentations from the start of REN001-201 will include all mtDNA-PMM subjects who receive at least one dose of

study drug in REN001-201 and will continue to acknowledge the randomization to treatment groups at the start of REN001-201.

Presentations from the start of REN001 treatment will summarize the data emergent during treatment with mavodelpar. These summaries will include all mtDNA-PMM subjects who receive mavodelpar in REN001-201 and/or REN001-202. In addition to these summaries, data from REN001-202 alone will be reported which will include mtDNA-PMM and nDNA-PMM subjects. These datasets will provide long-term safety, as well as descriptive information on efficacy measures.

As described in [Section 3.3](#) there are 4 pathway options in which subjects can enter REN001-202. The pathway options are described in more detail below:

1. REN001-201 W24

The majority of subjects enrolling in REN001-202 will enroll at REN001-201 Week 24. This will prevent an interruption in dosing and reduce the number of study visits and assessments for subjects.

The REN001-201 Week 24 visit will also be the REN001-202 Baseline visit; data in the REN001-201 database for this visit will be copied across programmatically to the REN001-202 database to avoid sites having to re-enter the data. Any data from REN001-201 database repeated in the REN001-202 database will be removed from the tables, listings and analysis datasets prior to reporting the combined data from the two studies. For example, any ongoing AEs or medications at the REN001-201 Week 24 visit will be copied across to the REN001-202 database, where they may be updated if there is any status change (e.g., end date being available); hence the latest information on these events recorded in REN001-202 database will be used for reporting.

Dosing in REN001-202 will start the day after the REN001-201 Week 24 visit. However, to allow for scheduling of eye examinations and DXA scans these REN001-201 Week 24 assessments can occur up to 14 and 28 days respectively, after the first dose of study drug in REN001-202.

The schematic below details how subjects transition between the 2 studies and the visit naming convention throughout the 2 studies:

REN001-201 Treatment Group	REN001-201							REN001-202						
		Sc	BL	W2	W4	W12	W18	W24 BL	M1	M3	M6	M12	M18	M24
REN001	REN001							REN001						
	Sc	BL	M0.5	M1	M3	M4.5	M6	M7	M9	M12	M18	M24	M30	M54
Placebo	Placebo							REN001						
	Sc	BL	M0.5	M1	M3	M4.5	M6 *BL	M7 *M1	M9 *M3	M12 *M6	M18 *M12	M24 *M18	M30 *M24	M54 *M48

Footnote: Sc=Screening; BL=Baseline; FU=Follow-up; W=Week; M=Month.

* Baseline visit and nominal visits from start of REN001 treatment.

In REN001-202 visits occur every 6 months between Month 24 and Month 48 (i.e., Months 30, 36 and 42). Where applicable, a final follow up telephone call will occur approximately 30 days after the last dose of study drug.

2. REN001-201 FU

Subjects who enroll at the REN001-201 FU visit will have had an interruption in study drug from the time of the REN001-201 Week 24 visit to the time of the combined REN001-201 FU and REN001-202 Baseline visits. This gap in study treatment is expected to be approximately 4 weeks. For reporting purposes, the nominal study visits in REN001-202 will be considered as a continuation from REN001-201 Week 24.

The REN001-202 Baseline visit data will either be collected at the visit or come from the REN001-201 FU visit if the assessment is performed at the FU visit. The exception to this is the eye examinations and DXA scans which will be taken from REN001-201 Week 24 visit; however, to allow for scheduling of eye examinations and DXA scans these REN001-201 Week 24 assessments can occur after the first dose of study drug in REN001-202. As above for REN001-201 W24 rollover subjects, data in the REN001-201 database for the FU visit will be copied across programmatically to the REN001-202 database to avoid sites having to re-enter the data. Any data from REN001-201 database repeated in the REN001-202 database will be removed from the tables, listings and analysis datasets prior to reporting the combined data from the two studies. For example, any ongoing AEs or medications at the REN001-201 FU visit will be copied across to the REN001-202 database, where they may be updated if there is any status change (e.g., end date being available); hence the latest information on these events recorded in the REN001-202 database will be used for reporting.

Dosing in REN001-202 will start on the day of the REN001-202 Baseline visit.

The schematic below details how subjects transition between the 2 studies and the visit naming convention throughout the 2 studies:

REN001-201 Treatment Group	REN001-201								REN001-202						
		Sc	BL	W2	W4	W12	W18	W24	FU BL	M1	M3	M6	M12	M18	M24
REN001	REN001								REN001						
	Sc	BL	M0.5	M1	M3	M4.5	M6		M7	M9	M12	M18	M24	M30	M54
Placebo	Placebo								REN001						
	Sc	BL	M0.5	W4	W12	W18	W24 *BL	→	M7 *M1	M9 *M3	M12 *M6	M18 *M12	M24 *M18	M30 *M24	M54 *M48

Footnote: Sc=Screening; BL=Baseline; FU=Follow-up; W=Week; M=Month.

* Baseline visit and nominal visits from start of REN001 treatment.

In REN001-202 visits occur every 6 months between Month 24 and Month 48 (i.e., Months 30, 36 and 42). Where applicable, a final follow up telephone call will occur approximately 30 days after the last dose of study drug.

3. (a) REN001-201 Exit

Enrolment after exiting REN001-201 will result in a break in study participation of variable duration where the subject is off study drug and not monitored in either study. Due to the gap in monitoring and dosing, for reporting purposes, the subject's two participations will be considered as two separate subjects and data in REN001-202 will not be considered as a continuation from REN001-201.

These subjects will need to complete Screening and Baseline visits in REN001-202 to check eligibility prior to enrolment. If the subject had a DXA scan in REN001-201, then the REN001-201 Week 24 visit can be used as the Baseline assessment if there is 6 months or less since the assessment. Similarly, the REN001-201 Week 24 eye examination can be used as the Baseline assessment if there is a gap of 6 months or less.

Dosing in REN001-202 will start on the day of the REN001-202 Baseline visit.

The schematic below details how subjects transition between the 2 studies:

REN001-201 Treatment Group	REN001-201								Break in study participation	REN001-202							
	Sc	BL	W2	W4	W12	W18	W24	FU		Sc	BL	M1	M3	M6	M12	M18	M24
REN001	REN001									REN001 [^]							
	Sc	BL	M0.5	M1	M3	M4.5	M6	FU		Sc	BL	M1	M3	M6	M12	M18	M24
Placebo	Placebo									REN001							
	Sc	BL	M0.5	W4	W12	W18	W24	FU		Sc	BL	M1	M3	M6	M12	M18	M24

Footnote: Sc=Screening; BL=Baseline; FU=Follow-up; W=Week; M=Month.

[^] Data from REN001-202 will not be considered a continuation of REN001-201 but will be reported as a separate subject. In REN001-202 visits occur every 6 months between Month 24 and Month 48 (i.e., Months 30, 36 and 42). Where applicable, a final follow up telephone call will occur approximately 30 days after the last dose of study drug.

3. (b) REN001-101

REN001-101 completed in March 2020 and therefore subjects will not have received mavodelpar for more than 2 years at the time of entry to REN001-202. For reporting purposes, only data from the start of REN001-202 will be considered.

Subjects will need to perform Screening and Baseline visits in REN001-202 to check eligibility prior to enrolment.

Dosing in REN001-202 will start on the day of the REN001-202 Baseline visit.

The schematic below details the subject visits:

REN001-201 Treatment Group	REN001-201								REN001-202							
	Sc	BL	W2	W4	W12	W18	W24	FU	Sc	BL	M1	M3	M6	M12	M18	M24
NA	Not Applicable								REN001							
									Sc	BL	M1	M3	M6	M12	M18	M24

Footnote: Sc=Screening; BL=Baseline; FU=Follow-up; W=Week; M=Month; NA=Not Applicable.

In REN001-202 visits occur every 6 months between Month 24 and Month 48 (i.e., Months 30, 36 and 42). Where applicable, a final follow up telephone call will occur approximately 30 days after the last dose of study drug.

4. nDNA-PMM Subjects

Subjects enrolled with nDNA-PMM will not have received mavodelpar previously so only data from the start of REN001-202 will be available to report.

Subjects will need to perform Screening and Baseline visits in REN001-202 to check eligibility prior to enrolment. Dosing in REN001-202 will start on the day of the REN001-202 Baseline visit.

The schematic below details the subject visits:

REN001-201 Treatment Group	REN001-201								REN001-202								
	Sc	BL	W2	W4	W12	W18	W24	FU	Sc	BL	M1	M3	M6	M12	M18	M24	M48
NA	Not Applicable								REN001								
	Sc	BL	M1	M3	M6	M12	M18	M24	M48								

Footnote: Sc=Screening; BL=Baseline; FU=Follow-up; W=Week; M=Month; NA=Not Applicable.
 In REN001-202 visits occur every 6 months between Month 24 and Month 48 (i.e., Months 30, 36 and 42).
 Where applicable, a final follow up telephone call will occur approximately 30 days after the last dose of study drug.

4. EFFICACY ASSESSMENTS

The sections below detail the efficacy assessments, including any derivations required for the efficacy secondary endpoints. The descriptive presentations of data regarding these endpoints are detailed in [Section 10](#).

Details concerning the baseline used in the derivation of changes from baseline are provided in [Section 8.6](#).

4.1. 12-MINUTE WALK TEST (12MWT)

In REN001-201 subjects will perform the 12MWT at Screening, Baseline, Week 12 (Month 3) and Week 24 (Month 6). In REN001-202 subjects will be assessed at Baseline, Months 3, 6, 12, 18 and 24; which from the start of REN001-201 are equivalent to Months 6, 9, 12, 18, 24 and 30. It will also be assessed at an early termination visit if the subject withdraws from the study. In addition, nDNA-PMM subjects will have a screening 12MWT assessment.

The test measures the distance a subject can walk on a flat, hard surface in a period of 12 minutes. To reduce site variability sites will be fully trained to administer the test according to the REN001-202 exercise manual. If the subject does not walk for the full 12 minutes, the distance walked and the duration of time walked will be recorded, along with the reason for stopping prematurely.

Handling of missing or incomplete 12MWT are detailed in [Section 8.3.1](#).

For each visit changes from baseline and percent changes from baseline will be calculated.

Additionally, the exploratory endpoints, distance walked in the first 6 minutes (from start of test up to 6 minutes) and the last 6 minutes (>6 minutes up to 12 minutes) will be derived. As only the number of completed laps are recorded each minute with the final minute recording any partial lap ongoing at the end of the 12 minutes, the distance walked in the first 6 minutes will be the total number of completed laps multiplied by the lap distance (20 meters). The distance walked in the last 6 minutes will then be the total distance walked minus the distance walked in the first 6 minutes. Note, in most cases, this will be an underestimate of the distance walked in the first 6 minutes and an over-estimate of the distance walked in the last 6 minutes.

Pre and post exercise measurements for heart rate and blood pressures are collected. The changes (post – pre) will be calculated.

4.2. PATIENT-REPORTED OUTCOMES MEASUREMENT INFORMATION SYSTEM (PROMIS) SHORT FORM – FUNCTIONAL ASSESSMENT OF CHRONIC ILLNESS THERAPY (FACIT) FATIGUE 13A

The PROMIS short form - FACIT Fatigue 13a is a set of person-centered measures that evaluate a range of fatigue symptoms, from mild subjective feelings of tiredness to an overwhelming, debilitating, and sustained sense of exhaustion that likely decreases a subject's ability to execute daily activities and function normally in family or social roles. The fatigue short forms are universal rather than disease specific. All assess fatigue over the past 7 days.

In REN001-201 the PROMIS questionnaire will be used at Screening, Baseline, Week 4 (Month 1), Week 12 (Month 3), Week 18 (Month 4.5) and Week 24 (Month 6). In REN001-202 subjects will be assessed at Baseline, Months 1, 3, 6, 12, 18 and 24; which from the start of REN001-201 are equivalent to Months 6, 7, 9, 12, 18, 24 and 30. It will also be assessed at an early termination visit if the subject withdraws from the study.

There are 13 questions on a 5-point scale ranging from not at all (1) to very much (5). All questions, except Questions 7 and 8, are scaled so that a higher score indicates a greater impact on fatigue. Answers to Questions 7 and 8 will be reversed prior to analysing. The total score is derived by summing the scores and will have a range from 13 to 65. If a subject has a missing response, then the total score will not be derived.

The T-score will be determined using the HealthMeasures Scoring Service (https://www.assessmentcenter.net/ac_scoringservice) (PROMIS 2019). This service uses "response pattern scoring" (Expected A Posteriori estimation) and will also derive a T-score when there is missing data. Subject ID and Visit will be de-identified in the dataset prior to using this scoring service. The T-score rescales the total score into a standardized score, relative to the US general population, with a mean of 50 and a standard deviation of 10. Therefore, an individual with a T-score of 60 is one standard deviation (SD) worse than the mean of the US general population.

For each visit changes from baseline will be calculated for the T-score and total score. The total score data will only be listed.

4.3. PATIENT GLOBAL IMPRESSION OF CHANGE (PGIC) – MUSCLE SYMPTOMS AND FATIGUE SYMPTOMS

In REN001-201 the subject is asked to rate their change in PMM muscle symptoms and their PMM fatigue symptoms at Week 24 (Month 6). In REN001-202 subjects will be assessed at Months 12, 24, 36 and 48; which from the start of REN001-201 are equivalent to Months 18, 30, 42 and 54. It will also be assessed at an early termination visit if the subject withdraws from the study.

The PGIC has a 7-point scale from ‘Very Much Improved’ to ‘Very Much Worse’. This will be converted to a numeric scale from 3 (very much improved) to -3 (very much worse); hence a value of 0 will mean no change in muscle symptoms.

4.4. PATIENT GLOBAL IMPRESSION OF SEVERITY (PGIS) SCORE - MUSCLE SYMPTOMS AND FATIGUE SYMPTOMS

In REN001-201 the PGIS will be used at Screening, Baseline, Week 4 (Month 1), Week 12 (Month 3), Week 18 (Month 4.5) and Week 24 (Month 6). In REN001-202 subjects will be assessed at Baseline, Months 1, 3, 6, 12, 18, 24, 30, 36, 42 and 48; which from the start of REN001-201 are equivalent to Months 6, 7, 9, 12, 18, 24, 30, 36, 42, 48 and 54. It will also be assessed at an early termination visit if the subject withdraws from the study.

The subject will be asked to rate the severity of their PMM for muscle symptoms and for PMM fatigue symptoms over the past 7 days. The scale has 5 levels from ‘Absent’ to ‘Very Severe’.

For each visit changes from baseline will be calculated for the two symptom scores.

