Physician-PMM phenotypic description				X		X			X	X	X
Physical exam ³ (inc. weight)			X	X	X	X	X	X	X	X	X
ECG			X	X	X	X	X	X	X	X	X
Vital signs		X	X	X	X	X	X	X	X	X	X
Safety bloods haematology/biochemistry		X	X	X	X	X	X	X	X	X	X
HbA1c						X			X	X	X
Blood for bone and calcium markers				X		X		X	X	X	X
PK blood sample for REN001 ⁴		X	X	X	X	X	X	X	X	X	X
Urinalysis inc. pregnancy testing ⁵		X	X	X	X	X	X	X	X	X	X
Urine drugs of abuse		X	X	X	X	X	X	X	X	X	X
Serum FSH ⁶		X ⁷	X	X	X	X	X	X	X	X	X
Urine NTX bone markers		X	X	X	X	X	X	X	X	X	X
PROs ⁸		X	X	X	X	X	X	X	X	X	X
12MWT			X	X	X	X	X	X	X	X	X
Eye examination			X	X	X	X	X	X	X	X	X
DXA Scan ⁹									X	X	X
Dispense Study Drug			X	X		X		X	X	X	
Concomitant medication review	X										X
AE review	X										X
Dosing of study drug	X		X	X	X	X	X	X	X	X	X

¹ See Table 2. It is expected that most subjects will enrol at the STRIDE Week 24 visit with the baseline visit for this study coinciding with the STRIDE Week 24 visit. With additional assessments subjects can also enrol at the STRIDE FU visit, or at any time after exiting Study REN001-101 or STRIDE, and nDNA-PMM subjects (Table 2 and Section 6.1).

² If subject discontinues study drug, they will be required to attend an early withdrawal visit as soon as possible after their last dose of study drug. A FU telephone call by the site approx. 30 (±7) days after last dose of study drug is required unless subject transfers to commercially available mavodelpar. Clinically significant abnormalities should be followed up until resolved/stabilized.

³ Brief symptom directed physical exam can be done post baseline.

⁴ PK samples (1 or 2) will be collected at all visits except Month 3 when 4 PK samples will be collected at 0,1,2,4 hrs post dose.

⁵ Urine home pregnancy test kits will be supplied to WOCCBP to enable monthly pregnancy testing. The study centre must contact the subject to confirm the pregnancy test results. The final test will be performed prior to the follow-up telephone contact approximately 30 days after the last dose of study drug.

⁶ FSH test should be done during study if menopausal symptoms develop.

⁷ FSH to be measured for all females (aged ≥45 years) not confirmed as post-menopausal.

⁸ PROs include MFIS, PGIS and PGIC (muscle and fatigue symptoms), SF-36, PROMIS, WPAI:SHP, BPI. BPI will be carried out at Month 12 and Month 24 only. After the M24 visit, only the PGIS will be conducted at each visit. The PGIC will be carried out at Month 12, 24, 36 and 48 only.

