7.3.3 Patient Global Impression of Change (PGIC): Muscle and Fatigue

7.3.3.1 Muscle Symptoms

The subject will be asked to rate their degree of improvement or worsening of PMM muscle symptoms compared to before the start of study drug in this open label study, using a 7-point scale, standardized PGIC scale.

Overall, how would you rate the change in the severity of your muscle symptoms related to your Primary Mitochondrial Myopathy **since starting the study**?

- a. Very much improved
- b. Moderately improved
- c. Minimally improved
- d. No change

- e. Minimally worse
- f. Moderately worse
- g. Very much worse

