7.3.3.2 Fatigue Symptoms

The subject will be asked to rate their degree of improvement or worsening of PMM fatigue symptoms compared to before the start of study drug in this open label study, using a 7-point scale, standardized PGIC scale.

Overall, how would you rate the change in the severity of your fatigue symptoms related to your Primary Mitochondrial Myopathy **since starting the study**?

- a. Very much improved
- b. Moderately improved
- c. Minimally improved
- d. No change
- e. Minimally worse
- f. Moderately worse
- g. Very much worse

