APPENDIX 2 – REN001-201 SCHEDULE OF ASSESSMENTS

Time and Events Table	Screening	Baseline ^{1,2} (Day 1)	Week 2 ³ (Day 14)	Week 4 ³ (Day 28)	Week 8 (Day 56)	Week 12 ^{2,4} (Day 84)	Week 16 (Day 112)	Week 18 ³ (Day 126)	Week 20 (Day 140)	Week 24 ^{2,4} (Day 168)	Early Termn ^{2,5}	Follow Up ³ (21-28 days post last dose)
Visit number	1	2	3	4	5	6	7	8				
Window (days)			±3	±3	±7	±7						
Informed Consent ²⁰	X											
Completion of Proforma and data entered into eCRF ⁶	X											
Demographics	X											
Medical/medication/drug/alcohol/tobacco history ⁷	X											
Physician completion of PMM phenotypic description		X								X	X	
Physical exam ⁸	X	X				X				X	X	
12-lead ECG	X	X				X				X	X	
Supine Vital signs (BP, PR and temperature)	X	X	X	X				X		X	X	X
Serum FSH ⁹	X											
HbA1c	X									X	X	
Hepatitis B/C/HIV	X											
Safety labs (inc. urinalysis)	X	X ¹⁰	X	X		X		X		X ¹¹	X	X ¹¹
Blood sample for bone and calcium markers		X				X				X	X	
Pregnancy Test (WOCBP only) ¹²	X	X		X	X	X	X		X	X	X	X
Blood sample for genotyping ¹³	X											
Population PK blood sample ¹⁴		X	X	X		X		X		X	X	
Urine drugs of abuse	X	X				X				X	X	

Time and Events Table	Screening	Baseline ^{1,2} (Day 1)	Week 2 ³ (Day 14)	Week 4 ³ (Day 28)	Week 8 (Day 56)	Week 12 ^{2,4} (Day 84)	Week 16 (Day 112)	Week 18 ³ (Day 126)	Week 20 (Day 140)	Week 24 ^{2,4} (Day 168)	Early Term ^{2,5}	Follow Up ³ (21-28 days post last dose)
Urine NTX		X				X				X	X	
Sites to provide appropriate snacks and lunch	X	X				X				X	X	
Pedometer eDiary data collection (inc. review)	X	X ¹⁵	X			X		X		X		
MFIS / PGIS (muscle symptoms), PGIS (fatigue symptoms) and PROMIS – Short form FACIT fatigue 13a	X	X	X			X		X		X	X	
SF-36 / BPI and WPAI:SHP		X	X			X		X		X	X	
PGIC (muscle symptoms) and PGIC (fatigue symptoms)										X	X	
12 Minute Walk Test	X ¹⁶	X				X				X	X	
30STS		X				X				X	X	
IMP Capsule Counts			X	X		X		X		X	X	
Eye examination	X ¹⁷					X				X	X	
Wrist radiograph	X ¹⁸											
DXA Scan (REN001-201-DXA sub-study) ²¹	X									X	X	
Concomitant medication review	X											X
Dosing		X ¹⁹									X	
AE collection and reporting	X											X

1. Screening visit must take place a maximum of 8 weeks before the Baseline visit.
2. If appropriate and feasible Baseline, Week 12, Week 24 /Early Termination visits may be conducted over 2 days at the Investigators discretion.
3. In countries where the regulatory body allows, visit may be in the Study Center or a home nursing visit.

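### On the start-of-REN001-201 time axis, PGIC ratings with two different reference points share one display, which can make the early-start arm look worse from Month 18

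*SAP*

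**What the plan says.** **Reference point in REN001-202.** Protocol 7.3.3.1 has subjects rate muscle symptoms "compared to before the start of study drug in this open label study". Protocol 7.3.3.2 does the same for fatigue: "worsening of PMM fatigue symptoms compared to before the start of study drug in this open label study". The printed question is looser and says only "since starting the study".

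**Collection times.** In REN001-201, PGIC is collected at Week 24 or early termination (SAP Appendix 2, row "PGIC (muscle symptoms) and PGIC (fatigue symptoms"). In REN001-202 the footnote to Protocol Table 3 says "The PGIC will be carried out at Month 12, 24, 36 and 48 only"; the early withdrawal visits add a rating for subjects who stop. Neither study has a PGIC at baseline.

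**Combined axis.** SAP 4.3 places the REN001-202 ratings at times "which from the start of REN001-201 are equivalent to Months 18, 30, 42 and 54". It codes the scale from 3 to -3, "hence a value of 0 will mean no change in muscle symptoms", without saying since when.

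**Displays.** SAP 8.2 produces every summary under each of three approaches unless an exception is stated, and splits the start-of-REN001-201 approach by REN001-201 arm. SAP 10 applies that approach to efficacy. SAP 10.3 plans by-visit categorical tables and stacked bars for PGIC and states no exception.

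**Purpose.** SAP 2 says the start-of-REN001-201 presentation gives insight into the effect of starting mavodelpar six months later.

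**The concern.** Adding six months aligns the visits in time, but it does not align what the rating measures. Month 6 records change up to the end of the randomized period. By the protocol's definition, Months 18 to 54 record change since open-label dosing began. Placed in one table or row of bars, these look like a single trajectory.

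The arms are not affected equally. A subject who improved on REN001 in REN001-201 and stayed improved should answer 'No change' at Month 18. A placebo subject who made the same improvement after switching should answer 'improved'. Read as an early-versus-delayed comparison, the display would favour the delayed arm even if both arms had reached the same state. That is the comparison for which SAP 2 offers this presentation.

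SAP 8.6 deals with this for scales that have a baseline value by changing the baseline. PGIC is itself a retrospective change rating, so there is nothing to re-base.

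**Working it through.** **1. The plan's own mapping.** 12, 24, 36, 48 + 6 = 18, 30, 42, 54. In days: 336, 672, 1008, 1344 + 168 = 504, 840, 1176, 1512; dividing by 28 gives 18, 30, 42, 54. The relabelling is arithmetically correct.

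**2. Can Month 6 share the open-label reference?** No. For Week 24 enrollers, SAP 3.8 states "Dosing in REN001-202 will start the day after the REN001-201 Week 24 visit". Those entering at the follow-up visit start about four weeks later. The REN001-201 item wording is not in the documents, but its timing alone rules out the open-label reference.

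**3. How much of the display is involved.** Scheduled PGIC time points on this axis are Months 6, 18, 30, 42 and 54. Four of the five carry the open-label reference. Bars: 5 visits x 2 arms x 2 symptom domains = 20, of which 4 x 2 x 2 = 16 carry it. An early-termination rating from REN001-202 could also be windowed to a visit before Month 18 (SAP 8.4).

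**4. Direction.** Let T_E and T_D be the total change since the start of REN001-201 in the early- and delayed-start arms, and b_R and b_P the change already present in each when open-label dosing begins. With the protocol's reference, the ratings measure T_E - b_R and T_D - b_P, so the contrast is

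(T_E - T_D) - (b_R - b_P).

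The true contrast is displaced by -(b_R - b_P). This is against the early-start arm if b_R > b_P, zero if they are equal, and reversed if b_R < b_P. For example, a true retained advantage of 0.25 category is hidden completely when b_R - b_P = 0.25, and reversed when it is 0.5 (0.25 - 0.5 = -0.25).

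**5. Hypothetical size.** All inputs here are assumptions. Change is taken as normal, with one unit equal to one PGIC category and cut points at ±0.5, ±1.5 and ±2.5. Placebo change in REN001-201 is 0 (b_P = 0); REN001 benefit is 0.5 and maintained (b_R = T_E = 0.5); switchers catch up fully (T_D = 0.5); SD is 0.8; everyone uses the protocol's reference. The true contrast is 0. The displayed means are 0 (REN001 arm) and 0.5 (placebo arm).

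| Month 18 category | REN001 arm, % | Placebo arm, % |
|---|---|---|
| Very much worse | 0.1 | 0.0 |
| Moderately worse | 3.0 | 0.6 |
| Minimally worse | 23.6 | 9.9 |
| No change | 46.8 | 39.4 |
| Minimally improved | 23.6 | 39.4 |
| Moderately improved | 3.0 | 9.9 |
| Very much improved | 0.1 | 0.6 |

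Displaced share = half the sum of the absolute differences between the two columns = 23.4%. Varying the inputs:

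| Benefit (categories) | SD 0.8 | SD 1.2 | SD 0.8, half of subjects anchor to REN001-201 | SD 1.2, half of subjects anchor to REN001-201 |
|---|---|---|---|---|
| 0.25 | 11.1% | 7.9% | 5.6% | 4.0% |
| 0.5 | 23.4% | 16.2% | 11.7% | 8.1% |
| 1 | 46.8% | 32.3% | 23.4% | 16.2% |

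If all subjects anchor to REN001-201, or if the benefit is 0, every entry is 0.

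**6. Is another display available?** PGIS is collected at baseline and, on this axis, at Months 1, 3, 4.5, 6, 7, 9, 12, 18, 24, 30, 36, 42, 48 and 54 (SAP 4.4). That covers all five PGIC visits and the same two symptom domains. SAP 10.4 already plans shifts from baseline.

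**The case against.** The strongest reply is that the harm is conditional and small. The documents give no REN001-201 result, so b_R > b_P is unknown. The printed question does not name the study, so roll-over subjects may think back to REN001-201. No testing is planned, and SAP 2 already tells the reader to treat efficacy descriptively. Table shells are a separate document and may carry a footnote. PGIS already offers a sound delayed-start reading. The start-of-REN001-202 display would still set former placebo and former REN001 subjects side by side, with different groupings.

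Much of this is fair and limits the claim. Two refinements also stand:

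- Under the illustration's assumption of no placebo change in REN001-201, only the 8 REN001-arm bars (4 visits x 2 domains) actually move; 16 is the number carrying the open-label reference.
- Subjects entering at the follow-up visit are anchored after about four weeks off drug, and any benefit lost in that gap shrinks the shift. With assumed b_R = 0.75 and b_P = 0.25, 30% of the early arm entering this way and half their benefit lost, the mean shift is -(0.7 x 0.5 + 0.3 x (0.375 - 0.25)) = -0.39 instead of -0.50.

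What does not stand is that the existing caveat covers the problem. SAP 2 attributes the limits on efficacy to three causes: no randomized comparator, no blinding and informative missing data. A reader could not infer a changed reference point from these. Ambiguous wording is no defence either: mixed use puts two quantities in one bar, and uniform anchoring to REN001-201 would contradict the protocol's definition and mislabel the start-of-REN001-202 display. A footnote, if there is one, should follow from a rule in the SAP, which describes itself as the reference for the analyses in the clinical study report.

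**Conclusion.** The concern holds and should be fixed. That two reference points share one axis follows from the documents: 4 of 5 scheduled time points, or 16 of 20 scheduled bars, carry a reference that Month 6 cannot share. The shift against the early-start arm rests on two conditions the documents cannot settle: that subjects use the protocol's reference, and that REN001 gave more benefit than placebo in REN001-201. If both hold, the shift in mean rating equals that between-arm benefit. Under the hypothetical inputs with everyone on the protocol's reference, about 8% to 47% of subjects are displaced for benefits of 0.25 to 1 category. The consequence is confined to the descriptive reading of a secondary endpoint; no test, primary endpoint or safety conclusion changes.

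**What to change.** In SAP 4.3 and 10.3:

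- Limit PGIC in the start-of-REN001-201 presentation to ratings collected in REN001-201 (Week 24 and early termination).
- Show REN001-202 ratings, including early termination, only from the start of REN001-202 by entry group, labelled with the protocol's reference point. Note there that the printed item does not name the study, and that group differences reflect change since open-label start, not early versus delayed start.
- For the delayed-start question, point to the planned PGIS shifts from the REN001-201 baseline.

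If the combined display is kept, the minimum is to state the PGIC reference point for each study on it.

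The cost is about two sentences and one label. Every REN001-202 rating is still shown; what goes is the view of those ratings pooled by REN001-201 arm. SAP 12.3 sets a precedent by limiting DXA to two of the three presentations.
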